8.1.4.2 Guidelines for monitoring and management of CK

If at any time after Randomization a participant experiences a CK elevation $>5 \times$ ULN, the participant will undergo a repeat confirmatory assessment as soon as is reasonably possible, preferably within 3 to 7 days of the laboratory result becoming available.

A repeat CK assessment will include query for related symptoms.

If the repeat CK assessment confirms an unexplained (ie, not associated with recent trauma or physically strenuous activity) CK abnormality $>5 \times$ ULN and the participant is asymptomatic, he/she should receive further assessment and investigation into the cause, assessment of whether there is renal injury, and measurement of CK approximately weekly, or more frequently if clinically indicated, until resolution. If CK levels continue to rise, the study drug should be discontinued.

If the participant experiences a CK elevation $>5 \times$ ULN and is symptomatic, the following should be completed:

- Interruption of study drug;
- Clarification of the nature, duration, and intensity of muscle symptoms;
- Review of possible predisposing factors, such as unaccustomed exercise, heavy alcohol intake, and viral illness (consider performing serology);
- Evaluation for additional diagnoses or other conditions which can cause myopathy, including muscle tenderness (by physical examination), weakness, rash, measurement of serum creatinine, and/or dipstick urinalysis with microscopy, if indicated;
- Measurement of clinical chemistries to assess the possibility of lactic acidosis; and
- Follow-up of symptoms and CK until the abnormality has resolved.

If, based on the above evaluation, an alternative explanation is suspected, consideration can be given to resuming study drug once CK returns to Baseline levels.

If no alternative explanation exists, consideration should be given to withdrawing the participant from study drug treatment.

If the repeat CK assessment confirms an unexplained (ie, not associated with recent trauma or physically strenuous activity) CK $>10 \times$ ULN, the participant should be withdrawn and given no further doses of study drug, even in the absence of symptoms. The signs and symptoms and laboratory assessments as outlined above should also be evaluated. The participant should continue being followed in the study for safety.

Any event of rhabdomyolysis, regardless of CK, should lead to study drug interruption/discontinuation until the contribution of obicetrapib has been excluded.

8.1.4.3 Guidelines for monitoring and management of NODM

Diabetes mellitus may be newly diagnosed during the study as described in [Section 8.1.4](#). If a participant is newly diagnosed with diabetes mellitus during the course of the study, the Investigator will recommend referral for initial diabetes education and management by an appropriate healthcare provider (eg, diabetologist, endocrinologist, or primary care provider). Interventions for management may include diet and lifestyle counseling, self-monitoring of blood

glucose, oral glucose-lowering medications, injectable medications, or insulin as deemed necessary by the treating physician based on the level of hyperglycemia and relevant symptoms.

8.1.4.4 Guidelines for monitoring and management of significant changes in renal function

If at any time after Randomization a participant experiences ANY of the following, the participant will undergo a repeat confirmatory assessment as soon as is reasonably possible, preferably within 3 to 7 days of the laboratory result becoming available:

- A >25% decrease in eGFR from Baseline, calculated using the Chronic Kidney Disease Epidemiology Collaboration equation;
- An eGFR <30 mL/min/1.73 m², calculated using the Chronic Kidney Disease Epidemiology Collaboration equation; and/or
- An increase in serum creatinine of ≥ 0.3 mg/dL (≥ 26.5 μ mol/L) from Baseline.

In consultation with the Medical Monitor and/or nephrologist, if no alternative etiology is determined, the study drug should be discontinued if participants experience an unexplained, confirmed increase in serum creatinine of ≥ 0.3 mg/dL (≥ 26.5 μ mol/L) from Baseline or an unexplained, confirmed >25% decrease in eGFR from Baseline.

If any of these individual laboratory parameters are confirmed, such events of decline in renal function should be recorded as an ESI.

8.1.4.5 Guidelines for monitoring and management of changes to antihypertensive medication(s)

Any changes to antihypertensive medication(s) due to changes in blood pressure in those participants receiving antihypertensive medication(s) treatment at Baseline will be assessed by the Investigator, primary care physician, or other appropriate health care provider to assess for etiologies of blood pressure change, to confirm clinical safety of the participant, to assess the need for any AE or SAE reporting, and to arrange for appropriate medical follow-up.

8.1.4.6 Guidelines for management of macular degeneration

In cases of suspected macular degeneration or acute vision loss, participants will be referred for an ophthalmological consultation.

8.2 Serious Adverse Events

An AE or adverse reaction is considered serious if, in the view of either the Investigator or Sponsor, it results in any of the following outcomes:

- Death;
- A life-threatening AE;

Note: An AE or adverse reaction is considered “life-threatening” if, in view of either the Investigator or Sponsor, its occurrence places the participant at immediate risk of death. It does not include an event that, had it occurred in a more severe form, might have caused death.

- Requires hospitalization or prolongation of existing hospitalizations;

Note: Any hospital admission with at least 1 overnight stay will be considered an inpatient hospitalization. An emergency room or urgent care visit without hospital admission will not be recorded as an SAE under this criterion, nor will hospitalization for a procedure scheduled or planned before signing of informed consent, or elective treatment of a pre-existing condition that did not worsen from Baseline. However, unexpected complications and/or prolongation of hospitalization that occur during elective surgery should be recorded as AEs and assessed for seriousness. Admission to the hospital for social or situational reasons (ie, no place to stay, live too far away to come for hospital visits, respite care) will not be considered inpatient hospitalizations.

- A persistent or significant disability/incapacity or substantial disruption of the ability to conduct normal life functions;
- A congenital anomaly/birth defect; or
- An important medical event.

Note: Important medical events that do not meet any of the above criteria may be considered an SAE when, based upon appropriate medical judgment, they may jeopardize the participant and may require medical or surgical intervention to prevent 1 of the outcomes listed above. Examples of such medical events include allergic bronchospasm requiring intensive treatment in an emergency room or at home, blood dyscrasias or convulsions that do not result in inpatient hospitalizations, or the development of drug dependency.

8.3 SAE Reporting – Procedures for Investigators

Initial reports

All SAEs occurring from the time of informed consent until the end of study participation (up to 35 [± 7] days post last dose) will be reported, regardless of the Investigator's determination as to relatedness, to [REDACTED] within 24 hours of the knowledge of the occurrence. After the 35-day reporting window, any SAE that the Investigator considers related to study drug must be reported to [REDACTED] or the Sponsor/designee ([REDACTED]).

To report the SAE, complete the SAE form electronically in the EDC system for the study. If the event meets serious criteria and it is not possible to access the EDC system, send an email to [REDACTED] at [REDACTED] or call the [REDACTED] SAE reporting line (telephone number listed in [Section 8.6](#)), and fax/email the completed back-up paper SAE form to [REDACTED] (contact information listed in Section 8.6) within 24 hours of awareness. When the EDC system becomes available, the SAE information must be entered within 24 hours of the system becoming available.

Follow-up reports

The Investigator must continue to follow the participant until the SAE has subsided or until the condition becomes chronic in nature, stabilizes (in the case of persistent impairment), or the participant dies.

Within 24 hours of receipt of follow-up information, the Investigator must update the SAE form electronically in the EDC system for the study and submit any supporting documentation (eg, participant discharge summary or autopsy reports) to [REDACTED] via fax or

email. If it is not possible to access the EDC system, refer to the procedures outlined above for initial reporting of SAEs.

8.4 Pregnancy Reporting

If a participant becomes pregnant during the study, the Investigator is to stop dosing with study drug immediately and permanently. However, the participant should be encouraged to remain in the study and to follow-up for study visits. See [Section 4.3](#) for more details regarding withdrawal criteria and discontinuation of study drug.

A pregnancy is not considered to be an AE or SAE; however, it must be reported to [REDACTED] within 24 hours of knowledge of the event. [REDACTED] will then provide the Investigator/study site the Exposure In Utero (EIU) form (Part 1) for completion. The Investigator/study site must complete the EIU form (Part 1) and fax/email it back to [REDACTED]
[REDACTED]

If the female partner of a male participant becomes pregnant while the participant is receiving study drug, the Investigator should notify [REDACTED] as described above.

The pregnancy should be followed until the outcome of the pregnancy is known, whenever possible. Once the outcome of the pregnancy is known, the EIU form (Part 2) should be completed and faxed/mailed to [REDACTED]. If the outcome of the pregnancy meets the criteria for immediate classification as an SAE (ie, postpartum complication, spontaneous abortion, stillbirth, neonatal death, or congenital anomaly), the Investigator should follow the procedures for reporting an SAE.

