3 STUDY DESCRIPTION

3.1 Summary of Study Design

This study will be a multisite, placebo-controlled, double-blind, randomized, Phase 3 study in approximately 300 participants with a history of HeFH who are not adequately controlled by their lipid-modifying therapy to evaluate the efficacy, safety, and tolerability of obicetrapib. Informed consent will be obtained from participants before the initiation of any study-specific procedures.

Approximately 300 eligible participants will be randomized in a 2:1 ratio, respectively, to the following treatment groups:

- Obicetrapib group: One 10 mg obicetrapib tablet once daily; or
- Placebo group: 1 placebo tablet once daily.

At least 70% of the participants enrolled into this study must be taking HISs. HeFH diagnosis is defined by existing confirmation via genetic testing, WHO Criteria/Dutch Lipid Clinical Network Criteria with a score of >8 points, and/or Simon Broome Register Diagnostic Criteria.^{17,18} Starting on Day 1, each participant will self-administer their assigned study drug once daily until Day 365. During the Treatment Period, participants will return to the study site for efficacy and safety assessments. An End of Study (EOS) Visit will be conducted approximately 35 days after the participant's last dose of study drug, during which vital signs; limited serum chemistry, hematology, and coagulation parameters; pharmacokinetics (PK); concomitant medications; and AEs will be assessed.

The study will be governed by a Steering Committee, and a Data and Safety Monitoring Board (DSMB) will provide independent oversight of participant safety.

The responsibilities, procedures, and workflow for these committees will be defined in separate charters outside of the protocol.

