4 SELECTION AND WITHDRAWAL OF PARTICIPANTS

4.1 Inclusion Criteria

Participants who meet all of the following criteria will be eligible to participate in the study:

1. Are willing and able to give written informed consent before initiation of any study-related procedures and willing to comply with all required study procedures;
2. Are male or female and ≥ 18 years of age at Screening;
 - o Females may be enrolled if all 3 of the following criteria are met:
 - They are not pregnant;
 - They are not breastfeeding; and
 - They do not plan on becoming pregnant during the study.
 - o Females of childbearing potential must have a negative urine pregnancy test at Screening;
Note: Females are not considered to be of childbearing potential if they meet 1 of the following criteria as documented by the Investigator:
 - They have had a hysterectomy or tubal ligation at a minimum of 1 cycle prior to signing the informed consent form (ICF); or
 - They are postmenopausal, defined as ≥ 1 year since their last menstrual period for females ≥ 55 years of age or ≥ 1 year since their last menstrual period and have a follicle-stimulating hormone level in the postmenopausal range at Screening for females < 55 years of age.
 - o Females of childbearing potential must agree to use an effective method of avoiding pregnancy from Screening (Visit 1) until 35 days after the last dose of study drug. Males whose partners are of childbearing potential must agree to use an effective method of avoiding pregnancy from Screening (Visit 1) until 35 days after the last dose of study drug. Effective methods of avoiding pregnancy are contraceptive methods used consistently and correctly (including implantable contraceptives, injectable contraceptives, oral contraceptives, transdermal contraceptives, intrauterine devices, and barrier method) or sterile sexual partner.

3. Have a history of HeFH as defined by at least 1 of the following:
 - o Genotyping by a central laboratory;
Note: Confirmation by prior genetic testing is required (ie, genotyping is not a Screening assessment).
 - o Clinical assessment using the WHO Criteria/Dutch Lipid Clinical Network Criteria with a score of > 8 points, as specified in [Appendix C](#)¹⁷ and/or
 - o Meet the Simon Broome Register Diagnostic Criteria for definite or possible FH, as specified in [Appendix D](#)¹⁸

4. Are on maximally tolerated lipid-modifying therapy, as an adjunct to diet, defined as follows:
 - A statin at a maximally tolerated stable dose;

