2.3 Study Endpoints

2.3.1 *Primary Efficacy Endpoints*

The primary efficacy endpoint is the percentage change from Baseline to Day 84 in LDL-C in the obicetrapib group compared to the placebo group.

2.3.2 *Secondary Efficacy Endpoints*

The secondary efficacy endpoints include the following:

- Percentage change from Baseline to Days 180 and 365 in LDL-C in the obicetrapib group compared to the placebo group;
- Percentage change from Baseline to Days 84, 180, and 365 in ApoB in the obicetrapib group compared to placebo group;
- Percentage change from Baseline to Days 84, 180, and 365 in non-HDL-C in the obicetrapib group compared to placebo group;
- Percentage change from Baseline to Days 84, 180, and 365 in HDL-C in the obicetrapib group compared to placebo group;
- Percentage change from Baseline to Days 84 and 365 in Lp(a) in the obicetrapib group compared to placebo group;
- Percentage change from Baseline to Days 84, 180, and 365 in TC in the obicetrapib group compared to placebo group;
- Percentage change from Baseline to Days 84, 180, and 365 in TG in the obicetrapib group compared to placebo group.

2.3.3 *Exploratory Efficacy Endpoints*

The exploratory efficacy endpoints include the following:

- Individual responsiveness defined as the number of participants reaching on treatment LDL-C levels of <40 mg/dL (<1.04 mmol/L), <55 mg/dL (<1.42 mmol/L), <70 mg/dL (1.81 mmol/L), and <100 mg/dL (<2.59 mmol/L) at Days 84 and 365;
- Individual responsiveness defined as the number of participants reaching on treatment non-HDL-C levels of <85 mg/dL (<2.20 mmol/L), <100 mg/dL (<2.59 mmol/L), and <130 mg/dL (<3.37 mmol/L) at Days 84 and 365;

- Individual responsiveness defined as the number of participants reaching on treatment ApoB levels of <65mg/dL (<0.65 mmol/L), <80 mg/dL (<0.80 mmol/L), and <130 mg/dL (<1.30 mmol/L) at Days 84 and 365;
- Percentage change from Baseline to Day 84 and 365 in ApoA1 in the obicetrapib group compared to the placebo group; and
- Trough levels of obicetrapib from Baseline to Days 84, 180 and 365 in the obicetrapib group;

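### Protocol 8.4 requires notice of a partner pregnancy only if it begins while the male participant is receiving study drug, but contraception is required until 35 days after the last dose

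*Protocol*

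**What the plan says.** Four rules in the protocol bear on this.

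- **Partner pregnancy, Section 8.4.** "If the female partner of a male participant becomes pregnant while the participant is receiving study drug, the Investigator should notify" the safety contact, whose name is redacted. No period after dosing is given.
- **Contraception for male participants, Section 4.1, Inclusion Criterion 2 (same rule in the Synopsis).** "Males whose partners are of childbearing potential must agree to use an effective method of avoiding pregnancy from Screening (Visit 1) until 35 days", counted from the final dose.
- **Pregnancy in a participant, Section 8.4.** "If a participant becomes pregnant during the study, the Investigator is to stop dosing with study drug immediately and permanently". This trigger is the study, not the dosing period.
- **SAEs, Section 8.3.** "All SAEs occurring from the time of informed consent until the end of study participation" are to be reported, and the end of participation is put at up to 35 (±7) days after the last dose. After that, SAEs considered related to study drug must still be reported.

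Section 8.4 also separates pregnancy from the adverse-event route: "A pregnancy is not considered to be an AE or SAE; however, it must be reported to" the safety contact within 24 hours. A reported pregnancy is recorded on EIU Part 1, followed to outcome where possible, and closed on EIU Part 2. The SAP has no pregnancy-reporting rule.

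**The concern.** Two rules for the same men end on different dates. If a partner conceives ten days after the last dose, the man was still required to use contraception on that day, but Section 8.4 does not ask the investigator to notify anyone. With no notification, neither EIU form is triggered, and the pregnancy need not be followed to outcome.

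The partner rule is also the only one of the comparable windows that stops with dosing, and the protocol gives no reason. What is at stake is completeness of pregnancy-outcome data. Such data are few in a trial of about 300 participants, so each case counts. No efficacy result depends on it.

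**Working it through.** The plan states no figure to reproduce, so the check sets the windows side by side and counts days.

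**Windows**

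| Rule | Starts | Ends |
|---|---|---|
| Contraception, male participants (4.1) | Screening | 35 days after last dose |
| Pregnancy, female participants (8.4) | During the study | During the study |
| SAE reporting (8.3) | Informed consent | 35 (±7) days after last dose |
| AE collection (8.1) | Informed consent | EOS Visit, about 35 days after the End of Treatment Visit |
| Partner pregnancy (8.4) | While receiving drug | While receiving drug |

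**Length of the gap.** Let L be the day of the last dose. Contraception is required to day L + 35. Partner notification covers conceptions to day L. The difference is (L + 35) − L = 35 days, whatever L is.

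- Dosing to Day 365 (Section 5.1): 365 + 35 = Day 400, and 400 − 365 = 35 days not covered.
- Dosing stopped at Day 84: 84 + 35 = Day 119, and 119 − 84 = 35 days not covered.

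**Interruptions.** Section 4.3 allows temporary discontinuation and asks that it be considered before permanent discontinuation. SAP 3.3.7 plans to list interruptions longer than 14 days. On a literal reading, a man on interruption is not receiving study drug, so those days fall outside the partner rule too. A looser reading, in which he counts as on treatment until permanent discontinuation, is possible. The text does not choose between them.

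**Does another rule close the gap?**

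1. *AE/SAE collection.* No. Section 8.4 says that a pregnancy is neither an AE nor an SAE.
2. *Special situation reports (8.6).* No. The list covers overdose, misuse, abuse, medication error and adverse reactions linked to product complaints. Pregnancy is not on it.
3. *The general requirement in 8.4 that a pregnancy be reported.* Not clearly. It follows the paragraph about participants, and partner pregnancies then have their own, narrower sentence.
4. *Redactions in 8.4.* They stand where a recipient's name or contact would be, and nothing suggests that they hide a time window.
5. *Late discovery.* A conception during dosing that comes to light later is already covered, because the trigger is when the partner becomes pregnant. The gap concerns conceptions after the last dose.

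**Would the site be in contact?** Often yes. The protocol says "An End of Study (EOS) Visit will be conducted approximately 35 days after the" last dose, and Section 4.3 asks men who stop drug permanently to keep attending scheduled visits. A site may therefore learn of such a pregnancy and have no instruction to report it.

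**The case against.** The best defence is that both rules can be followed at once. A contraception period may be set cautiously and may reasonably run longer than a reporting trigger. The documents report no reproductive risk transmitted through the father. Section 8.4 does not forbid a report. A congenital anomaly is a seriousness criterion in Section 8.2, and Section 8.3 keeps the route open for related SAEs after the 35-day window. All of this stands, and it keeps the point minor. It does not remove the mismatch: the SAE route could bring in some serious outcomes, but it would not capture the pregnancy itself or start EIU follow-up.

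A reader might infer three stronger things that the documents do not support.

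- *That these pregnancies will be missed.* The text only fails to require the report.
- *That the 35 days are a period of drug exposure or washout.* The protocol does not use those terms for it. The contraception window opens at Screening, before any drug is taken, and no half-life is given, so residual exposure cannot be stated.
- *That the PK sample at the EOS Visit was meant to check this period and is left unused.* Protocol 3.1 only lists it among the assessments ("pharmacokinetics (PK); concomitant medications; and AEs will be assessed"). The SAP trough endpoint ("Trough levels of obicetrapib from Baseline to Days 84, 180 and 365 in the obicetrapib group") does not name it, but Protocol 9.2 and SAP 7 cover collected data at least by listing. Nothing ties the sample to pregnancy reporting.

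**Conclusion.** The inconsistency is real and minor. As written, partner conceptions in the 35 days after the last dose, and on a literal reading during interruptions, are not required to be reported or followed with the EIU forms. The contraception rule covers those 35 days, and the female-participant and SAE rules both run beyond the last dose.

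The size is a fixed 35 days for each man with a partner of childbearing potential, plus any interruption. Expressing it as a share of the contraception period would say nothing about how many pregnancies are affected, and the documents give no pregnancy rate or number of such men from which to estimate that. Alpha, power and the efficacy analysis are not affected.

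The conclusion assumes that the general reporting sentence in 8.4 refers to participants, and that the redacted text holds no time window. If the sponsor intended that sentence to cover partners without limit, the section should say so.

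**What to change.** Reconcile Section 8.4 with Inclusion Criterion 2, so that the partner-pregnancy sentence covers the same post-dose period as the contraception requirement. A cross-reference to that criterion would keep the two from drifting apart. State in the same sentence whether temporary interruptions count as receiving study drug for this purpose. The contraception rule and the dosing rules stay as they are, and the SAP needs no change.

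The cost is one phrase in a protocol amendment, notice to sites, and at most a few more pregnancies to follow to outcome.
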